5. STATISTICAL ANALYSIS METHODS

5.1. General Considerations

Descriptive statistical methods will be used to summarize the data from this trial. Unless stated otherwise, the term “descriptive statistics” refers to number of subjects (N), number of observations (n), arithmetic mean, median, standard deviation (SD), first quartile (Q1), third quartile (Q3), minimum, and maximum for continuous data, and frequencies and percentages for categorical data. Certain figure presentations will include the standard error of the mean (SE). The term “treatment group” refers to treatment assignment in Trial CVL-865-SZ-001: Placebo, 7.5 mg BID CVL-865, 25 mg BID CVL-865 and assignment in Trial CVL-865-SZ-002: 25 mg BID CVL-865. All data collected from subjects who sign the informed consent form, including screen failures, will be included in data listings. Unless otherwise noted, the data listings will be sorted first by treatment, subject number and then by date within each subject number.

5.2. Populations for Analyses

The analysis populations are defined ([Table 8](#)).

Table 8. Populations for Analysis

Population	Description	Analysis
Enrolled Set	All subjects who signed the informed consent form.	Disposition
Safety Set	All subjects that receive at least 1 dose of IMP.	Demographics, baseline characteristics and safety analysis
Efficacy Set	All subjects in the Safety Set who have at least 1 post-baseline seizure diary entry.	Exploratory analyses
PK analysis set	All subjects who receive at least 1 dose of IMP and have at least 1 measurable CVL-865 concentration	PK analysis

Abbreviations: IMP = investigational medicinal product, PK = pharmacokinetic.

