## **7.3 Individual Subject Discontinuation**

After treatment assignment, a subject may stop treatment permanently for a variety of reasons. Treatment discontinuations may be initiated by a subject who is not satisfied with treatment or may become medically necessary due to AEs, required treatment with a disallowed medication or therapy, or other issues, as determined by the investigator.

Subjects should begin the Taper Phase at the time the decision is made to discontinue. All Taper Phase and Post-treatment Follow-up procedures should be performed as indicated in the Schedules of Assessments ([Table 2](#) and [Table 3](#)). Under certain circumstances, when subjects leave the trial early, dosing with the taper medication or continuing with the taper phase medication may be inadvisable. The decision not to taper the subject is upon agreement from the medical monitor. If the taper will not be utilized, then all assessments required at Visit 17 should be conducted approximately 30 days following the last dose.

For subjects who early terminate prior to Day 15 (prior to the Maintenance Phase), an alternate taper scheme may be used. This includes subjects who sign consent for CVL-865-SZ-002 but who are then determined to not meet eligibility criteria.

A subject will discontinue IMP for the reasons listed below:

- Any of the following AESIs

- Hemoglobin <8 g/dL
- WBC count <2.5 × 10^9/L
- Neutrophil count <1.5 × 10^9/L
- Platelet count <100 × 10^9/L
- Female subjects who have a positive pregnancy test result during the trial
- Withdrawal of consent
- Investigator's discretion (eg, including failure to comply with trial procedures or dosing)

All subjects have the right to withdraw their consent from further participation in the trial at any time without prejudice. Subjects cannot withdraw consent for use of data already collected as part of the trial, but only for future participation. The investigator can also discontinue a subject's participation in the trial at any time if medically necessary. Unless the subject provides their written withdrawal of consent or there is other written documentation by the investigator confirming the subject's verbal intent to completely withdraw from the trial, subjects should be followed for all protocol-specified evaluations and assessments, if possible.

Complete withdrawal of consent requires a subject's refusal of ALL of the following methods of follow-up:

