### **9.3 Populations for Analyses**

The following data sets are defined for analysis:

- Enrolled Set: comprises all subjects who consent to participate in the clinical trial (ie, sign the ICF for Trial CVL-865-SZ-002)
- Safety Set: comprises all subjects that receive at least 1 dose of IMP in Trial CVL-865-SZ-002
- Efficacy Set: comprises all subjects in the Safety Set who have at least 1 post-baseline efficacy evaluation

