4.1.2. Screen Failures

Screen failures are defined as subjects who consent to participate in this clinical trial but are deemed not eligible or withdraw consent prior to receiving IMP in Trial CVL-865-SZ-002. Receiving IMP defined as any IMP taken after the ICF has been signed by the subject.

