5.11. Exploratory Efficacy Analyses

5.11.1. Exploratory Efficacy Endpoints

The exploratory efficacy endpoints are:

- Focal onset seizure frequency per week over the Maintenance Phase and change from baseline
- Focal onset seizure frequency per 8 week period over the Maintenance Phase and change from baseline
- Seizure freedom
- Seizure rate over time
- PGI-C score at each trial visit
- Change from Baseline in CGI-S score at each trial visit

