5.11.2. Exploratory Efficacy Analysis Approach

All Exploratory Efficacy Analysis endpoints will be summarized on the Efficacy Set.

Descriptive statistics will be provided for each efficacy endpoint and will be summarized at each trial visit using available data. Focal onset seizure frequency per week and 8 week period over the maintenance phase will include change from baseline. Baseline is derived from Trial CVL-865-SZ-001 and will be adjusted to an appropriate frequency for comparison. Any period which does not maintain greater than 20% diary compliance will not be summarized. Seizure rate over time will be displayed as adjusted frequencies over the maintenance phase. CGI-S will be displayed separately as change from baseline and change from Double-Blind Baseline. Baseline (Extension) is defined as the last assessment prior to the initiation of IMP in CVL-865-SZ-002. Double-Blind Baseline will be the baseline value from study CVL-865-SZ-001.

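### SAP Table 8 narrows the Efficacy Set to subjects with a seizure diary entry and applies it to PGI-C and CGI-S, an undeclared departure from the protocol with a small expected effect

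*SAP*

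**What the plan says.** Protocol 9.3 defines the Efficacy Set in these terms: it "comprises all subjects in the Safety Set who have at least 1 post-baseline efficacy evaluation". The kind of evaluation is left open.

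SAP 5.2, Table 8, gives a different condition: "All subjects in the Safety Set who have at least 1 post-baseline seizure diary entry".

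SAP 5.11.2 then fixes where the set is used: "All Exploratory Efficacy Analysis endpoints will be summarized on the Efficacy Set". The endpoints listed in SAP 5.11.1 mix diary-based measures (seizure frequency, seizure freedom, seizure rate) with two rating scales: "PGI-C score at each trial visit" and the change from baseline in CGI-S.

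SAP section 6, on changes in the planned analyses, covers only future departures from the SAP itself. It lists no difference from the protocol.

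The Safety Set wording differs as well. The protocol says that it "comprises all subjects that receive at least 1 dose of IMP in Trial CVL-865-SZ-002"; Table 8 says "All subjects that receive at least 1 dose of IMP", without naming the trial.

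**The concern.** The PGI-C is a patient self-rating and the CGI-S an observer rating. Both are collected at visits, and nothing in protocol 8.2.2 and 8.2.3 or SAP 3.1.3 and 3.1.4 makes them depend on the diary. Under the SAP, a subject who attends visits and is rated, but never makes a diary entry in the extension, drops out of the PGI-C and CGI-S summaries. Under the protocol the same subject stays in.

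Two things are at stake. The protocol and the SAP can give a different n for the same PGI-C and CGI-S tables, and nothing tells the reader of the report why. The exclusion also depends on diary use, which is not what the scales measure. If subjects who abandon the diary fare differently from the rest, the two summaries lose the ratings that would show it.

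**Working it through.** The plan gives no figure to reproduce: the trial is descriptive, and its sample size is not based on power. The check is a comparison of texts, followed by a bound on the size of the effect.

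**Step 1. Classify subjects under each definition.** All four types are in the Safety Set.

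| Post-baseline diary entry | Post-baseline PGI-C or CGI-S | Protocol Efficacy Set | SAP Efficacy Set |
|---|---|---|---|
| Yes | Yes | In | In |
| Yes | No | In | In |
| No | Yes | In | **Out** |
| No | No | Out | Out |

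The definitions disagree in one row only. The SAP set lies inside the protocol set, so the change is a narrowing.

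**Step 2. What the diary condition does for each endpoint.**
- Seizure rate and frequency: SAP 3.1.1 divides the seizure count by the days with non-missing counts. With no diary entry the denominator is zero and no rate exists, so the condition is redundant here.
- Seizure freedom: SAP 3.1.2 defines it as no seizures in the maintenance period. Without a diary condition, a subject with no entries could be read as seizure-free, so the condition is useful here.
- PGI-C and CGI-S: the condition has no bearing on whether a rating exists or is valid. Its only effect is to remove ratings.

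**Step 3. Ratings at stake per subject.** The schedules (protocol Tables 2 and 3) place post-baseline PGI-C and CGI-S at Visits 2, 3, 5, 8, 11 and 15/ET. The maximum is 6 ratings per scale per excluded subject.

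**Step 4. Share of subjects.** About 120 subjects are expected to be eligible (protocol 9.2, SAP 1.2). If k have ratings but no entry, the share is k/120:
- k = 1: 1/120 = 0.8%
- k = 2: 2/120 = 1.7%
- k = 5: 5/120 = 4.2%, at most 5 × 6 = 30 ratings per scale

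The documents give no value for k, so these are illustrations.

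**Step 5. How likely is no entry at all?** Assume independent daily completion with probability c. The chance of no entry in the 14 days before Visit 2 (Day 15) is (1 − c)^14:
- c = 0.5: 0.5^14 = 0.006%
- c = 0.2: 0.8^14 = 4.4%
- c = 0.1: 0.9^14 = 22.9%

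Only one rating per scale falls due by then, and a single later entry brings the subject back into the set. Independence is a simplification: a subject who gives up the diary at rollover has no entries on any day. That is the realistic route into the disputed row.

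**Step 6. Effect on a summary mean.** Let d be the difference in mean rating between excluded and included subjects. The protocol-set mean minus the SAP-set mean is (k/N) × d. Taking d = 1 CGI-S category (assumed) and N = 120:
- k = 1: 0.008 × 1 = 0.008 points
- k = 5: 0.042 × 1 = 0.042 points

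At later visits N is smaller and the shift grows in proportion, but with few subjects in the disputed row it remains small.

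**The case against.** The case for leaving Table 8 alone has four parts. Protocol 9.4 assigns the description of analysis populations to the SAP. The threshold is a single entry in a diary that is kept daily and reviewed at every visit and contact, and subjects with substantial noncompliance in the double-blind trial are excluded (protocol 5.2), so almost nobody should fail it. The endpoints are exploratory, with no hypothesis. Excluded ratings would still appear in the listings (SAP 5.1).

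Most of this stands, and it is why the point is minor. It does not remove the mismatch. Protocol 9.3 had already defined the set, so a different definition in the SAP should be declared. A condition that almost never applies is also no reason to keep it for two scales on which it can only discard data.

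A reader might draw a stronger conclusion from the Safety Set row: that, with the trial number omitted, screen failures enter the primary safety denominator and dilute adverse event incidences. The route would be protocol 7.3, which allows an alternate taper scheme before Day 15 and adds: "This includes subjects who sign consent for CVL-865-SZ-002 but who are then determined to not meet eligibility criteria". Such a subject may take IMP after consent, and SAP 4.1.2 states: "Receiving IMP defined as any IMP taken after the ICF has been signed by the subject".

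The documents do not support that conclusion:
- Protocol 5.4 contains the same rule, attached to IMP in the extension trial. A taper-dosed ineligible subject has therefore received extension IMP under the protocol's wording too, and restoring the trial number does not change that subject's status.
- Where the SAP means double-blind dosing it says so (4.1.4, 4.1.7, 4.1.9, 4.1.17). Unqualified, IMP means extension IMP in the definitions of pre-treatment events, treatment-emergent events and prior medications (3.2.1.2, 3.2.1.3, 3.2.7.3), consistent with Day 1 in 4.1.3. If double-blind dosing counted, the pre-treatment category would be empty, because extension consent comes after that dosing.
- Any dilution figure would need a screen-failure rate and an incidence that the documents do not give.

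**Conclusion.** The Efficacy Set point holds. The SAP narrows a set that the protocol had defined, applies the narrower set to two scales that do not use the diary, and does not declare the change. This follows from the texts alone.

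Its size is small: probably zero to a few subjects, each 0.8% of about 120 and each with at most six ratings per scale, on exploratory descriptive summaries. That judgement assumes that few subjects attend visits without ever making a diary entry. The documents give no rate, but the compliance reviews make a large number unlikely. Severity is minor.

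The Safety Set difference is an omitted qualifier and nothing more. The inference that it alters the primary safety denominator should not be drawn.

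**What to change.** In SAP Table 8, return the Efficacy Set to the protocol's criterion of any post-baseline efficacy evaluation. In SAP 5.11.2, state that summaries of seizure frequency, seizure rate and seizure freedom are limited to Efficacy Set subjects with at least one post-baseline diary entry, and that PGI-C and CGI-S use the whole set. If the sponsor prefers the narrower set, declare it in SAP section 6 with the reason.

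For alignment only, add the extension trial number to the Safety Set row. Do not add a rule that discounts taper doses in subjects found ineligible. Neither document contains one, and it would move subjects exposed after consent from the primary safety tables into listings.

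The cost is a few lines of SAP text and one revised population flag, before database lock. No new data are needed.

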5.3. Statistical Hypotheses

There is no statistical hypothesis for this open-label trial.

5.4. Time of Analysis

A final analysis will be conducted once the last subject completes or discontinues the study, and the resulting clinical database has been cleaned, quality checked, the pre-analysis meeting has occurred, and the database has been locked.

No interim analyses are planned.

5.5. Multiplicity Adjustment

No adjustments for multiplicity are required as only descriptive statistics will be generated.

5.6. Strata and Covariates

No stratification was implemented in randomization.

5.7. Subject Disposition, Demographic and Baseline Characteristics

Subject disposition will be based on the Enrolled set population with tabulation of the number of subjects who complete the study, the number who discontinued from the study, reasons for discontinuation including the number of discontinues due to COVID-19 will be summarized. Additionally, the number of days on study for extension and double-blind will be summarized.

Number of subjects in each analysis population set will be summarized.

Demographic data and baseline characteristics including age, gender, childbearing potential, race, ethnicity and weight will be summarized using descriptive statistics for the Safety set.

5.8. Exposure to Treatment

The number of subjects who received IMP, treatment compliance, cumulative exposure to IMP (Double-Blind + Extension), days on IMP (Double-Blind and Extension), prematurely discontinued, and reason for IMP discontinuation will be summarized.

5.9. Medical History

Medical history events will be mapped to a Medical Dictionary for Regulatory Activities (MedDRA) version 27.1 or higher by preferred term and system organ class. Medical history will be summarized by treatment group using preferred terms and system organ classes. All events will be listed.

5.10. eDiary compliance

Exploratory efficacy variables are based on diary-collected seizure frequencies, and as such, diary compliance will be evaluated along with treatment compliance. Subjects are instructed to complete their diary entries at least once a day during the study. A diary day will be considered missing for compliance if a seizure diary record is missing for that day. Diary compliance will be evaluated during the Maintenance Phase and overall treatment period.

Diary compliance will be calculated as 100 times the number of diary days (i.e., days with completed diary assessments) during the period and dividing this quantity by the expected number of diary days that should have been completed during this period of time. Compliance is only computed for actual time of participation in the study up to the end of the Treatment Period. Only data prior to and on the date of last dose of study medication will be included in the compliance calculation. If a subject did not enter an analysis period, the diary compliance for the analysis period will not be calculated.

Diary compliance data will be listed and sorted by treatment group and subject.

5.11. Exploratory Efficacy Analyses

5.11.1. Exploratory Efficacy Endpoints

The exploratory efficacy endpoints are:

- Focal onset seizure frequency per week over the Maintenance Phase and change from baseline
- Focal onset seizure frequency per 8 week period over the Maintenance Phase and change from baseline
- Seizure freedom
- Seizure rate over time
- PGI-C score at each trial visit
- Change from Baseline in CGI-S score at each trial visit

5.11.2. Exploratory Efficacy Analysis Approach

All Exploratory Efficacy Analysis endpoints will be summarized on the Efficacy Set.

Descriptive statistics will be provided for each efficacy endpoint and will be summarized at each trial visit using available data. Focal onset seizure frequency per week and 8 week period over the maintenance phase will include change from baseline. Baseline is derived from Trial CVL-865-SZ-001 and will be adjusted to an appropriate frequency for comparison. Any period which does not maintain greater than 20% diary compliance will not be summarized. Seizure rate over time will be displayed as adjusted frequencies over the maintenance phase. CGI-S will be displayed separately as change from baseline and change from Double-Blind Baseline. Baseline (Extension) is defined as the last assessment prior to the initiation of IMP in CVL-865-SZ-002. Double-Blind Baseline will be the baseline value from study CVL-865-SZ-001.

5.12. Safety Analyses

The safety analysis will be conducted on the Safety Set.

Listings will be sorted such that all data collected for screen failed subjects will be grouped separately.

5.12.1. Adverse Events

Adverse events will be mapped to a Medical Dictionary for Regulatory Activities (MedDRA) version 27.1 or higher PT and SOC. If a subject experiences multiple events that map to a single PT, the greatest intensity and strongest investigator assessment of relation to IMP will be assigned to the PT for the appropriate summaries. Events with missing intensity or relationship will be classified as outlined in [Section 4.1.21](#). Summaries of TEAEs will include any AEs reported beginning with the initiation of study drug on Day 1 through last follow up contact. The occurrence of TEAEs will be summarized by PTs, SOCs, and intensity. Separate summaries of treatment-emergent serious adverse events (TESAEs), TEAEs related to IMP, TEAEs leading to death, AESIs (including those potentially related to abuse as assessed through the active monitoring of adverse events related to potential abuse and AEs involving medication handling

irregularities), AESIs not leading to discontinuation of IMP, TEAEs leading to the discontinuation if IMP and events leading to discontinuation of study will be generated respectively. A presentation of AEs by dose at event onset will be prepared. All adverse events reported will be listed for individual subjects showing both verbatim and PTs. All adverse events that occurred prior to the initiation of study will be excluded from the tables but will be included in the listings.

Missing onset dates will be imputed as previously outlined in [Section 4.1.22](#) as required to determine TEAEs.

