### 4 TRIAL DESIGN

#### 4.1 Overall Design

This is a 57-week, active-treatment, open-label extension trial designed to assess the long-term safety and tolerability of CVL-865 as adjunctive therapy in subjects with focal onset seizures. Enrollment into the trial will consist of eligible subjects who completed the Maintenance Phase of Trial CVL-865-SZ-001.

Eligible subjects will enter this trial directly after completing Visit 4 (end of Maintenance Phase) of Trial CVL-865-SZ-001. The efficacy and safety assessments from Visit 4 of Trial CVL-865-SZ-001 will serve as the baseline assessments for the open-label trial for any assessments that are not unique to the open-label trial. All subjects must provide informed consent to participate in the open-label trial before any baseline assessments that are unique to the open-label trial are performed.

This trial is designed with a maximum duration of approximately 61 weeks during which the subjects will receive CVL-865. The trial consists of the following:

- Up to 57-week Treatment Period consisting of the following:

- 2-week double-blind Titration Phase
- 52-week Maintenance Phase
- 3-week Taper Phase
- 4-week Follow-up Period

Following enrollment in Trial CVL-865-SZ-002, subjects will enter a 2-week double-blind Titration Phase. Based on the blinded treatment group subjects were assigned to in Trial CVL-865-SZ-001, the dose will be adjusted during the double-blind Titration Phase to a final dose of 25 mg BID as shown in [Table 4](#). Subjects who completed the Maintenance Phase of Trial CVL-865-SZ-001 on a dose of 25 mg BID will remain on this dose (blinded) for the Titration Phase of Trial CVL-865-SZ-002.

Subjects who terminate during the double-blind Titration Phase (before Day 15) should receive 3 weeks of IMP to complete the Taper Phase. Please refer to [Section 7.3](#).

Subjects will continue to receive treatment with CVL-865 25 mg BID throughout a 52-week Maintenance Phase. However, this daily dose of CVL-865 can be reduced to 17.5 mg BID to address tolerability issues upon investigator discretion. Following the Maintenance Phase, subjects will be tapered off investigational medicinal product (IMP) over 3 weeks. A summary of the dosing schedule is provided in [Table 4](#).

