### **8.4.1     *Time Period and Frequency for Collecting AE and SAE Information***

All AEs and SAEs will be collected from the signing of the ICF until the follow-up visit (Visit 17 at Day 428) at the time points specified in the Schedule of Assessments ([Table 2](#) and [Table 3](#)).

All SAEs will be recorded and reported to the medical monitor immediately and under no circumstance should this exceed 24 hours, as indicated in [Section 10.3](#) (Appendix 3). The investigator will submit any updated SAE data to the medical monitor within 24 hours of it being available.

Investigators are not obligated to actively seek AE or SAE after conclusion of the trial participation. However, if the investigator learns of any SAE, including a death, at any time after a subject has been discharged from the trial, and he/she considers the event to

be reasonably related to the IMP or trial participation, the investigator must promptly notify the sponsor.

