#### **9.4.1 Safety Analyses**

The safety analysis will be conducted on the Safety Set. The primary safety analysis is the frequency and severity of AEs during the Treatment Period. All AEs will be coded according to MedDRA preferred term. The incidence of treatment-emergent AEs (TEAEs) will include the following summaries:

- TEAEs by severity
- Drug-related TEAEs
- TEAEs with an outcome of death
- Serious TEAEs
- Discontinuations due to TEAEs

- TEAEs potentially related to abuse as assessed through the active monitoring of adverse events related to potential abuse and adverse events involving MHI

A TEAE is defined as an AE that started after the first dose of IMP in the open-label trial or a previously reported AE that increased in intensity, became serious, trial drug-related, or resulted in death, discontinuation, interruption, or reduction of IMP after the first dose of IMP in the open-label trial.

Other safety endpoints, including laboratory assessments, vital sign measurements, ECGs, medication withdrawal symptoms assessed by the mCIWA-B total scores at the scheduled visits and suicidality monitored during the trial using C-SSRS, will be summarized with descriptive statistics. Baseline is defined as the last assessment prior to the initiation of IMP in CVL-865-SZ-002. Additional presentations may be conducted evaluating changes from the original trial baseline. These analyses will be detailed in the statistical analysis plan.

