3.2.1.3. Treatment-emergent Adverse Event (TEAE)

Any event reported on the CRF that occurs on or after the initiation of IMP through the last follow up contact is considered treatment emergent. Additionally, it is assumed that an AE which was reported to have started on Day 1 without an associated onset time is assumed to be treatment emergent.

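### The protocol's primary safety analysis, AEs during the Treatment Period, has no table in the SAP, whose TEAE summaries all run to the last follow-up contact

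*SAP*

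**What the plan says.** Protocol Section 9.4.1, repeated in the synopsis, states: "The primary safety analysis is the frequency and severity of AEs during the Treatment Period". Section 4.1 defines that period: "Up to 57-week Treatment Period consisting of the following", namely titration, maintenance and a "3-week Taper Phase". The "4-week Follow-up Period" comes on top and brings the total to about 61 weeks.

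The TEAE definition in the same Section 9.4.1 has a start (the first dose in the extension) but no end. Protocol Section 8.4.1 collects AEs from consent to Visit 17 on Day 428.

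SAP Section 3.2.1.3 supplies an end: an event that "occurs on or after the initiation of IMP through the last follow up contact is considered treatment emergent". Section 5.12.1 applies the same window to the tables: "Summaries of TEAEs will include any AEs reported beginning with the initiation of study drug on Day 1 through last follow up contact". The tables cover preferred term, organ class, intensity, relatedness, seriousness, death, AESIs and discontinuation. None is limited to the Treatment Period or divided by phase. The section also promises a presentation of AEs by dose at onset, without giving its categories. SAP Table 3 defines the titration, maintenance and taper periods, but for efficacy data only, and has no follow-up row.

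**The concern.** The trial has no hypothesis and reports descriptive statistics only, so the AE tables are its main result. The protocol names one of them as primary and gives it a window. A programmer following the SAP would produce frequency and severity tables over a longer window and would not produce the named one.

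The first primary endpoint includes the temporality of TEAEs, and withdrawal symptoms are a separate endpoint under the same objective. For a ligand of the benzodiazepine site, an event on full dose, an event during taper and an event after the last dose have different meanings. Tables that run from first dose to last contact cannot tell them apart. A subject-level percentage over the longer window can only equal or exceed the Treatment-Period percentage, so the direction of any difference is known.

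**Working it through.** **1. The plan's own durations.** From Protocol Section 4.1: 2 + 52 + 3 = 57 weeks of treatment, and 57 + 4 = 61 weeks in total. From the Schedule of Assessments (Visit 16 on Day 400, Visit 17 on Day 428): 400 − 1 = 399 days = 57.0 weeks; 428 − 400 = 28 days = 4.0 weeks; 428 − 1 = 427 days = 61.0 weeks. The stated figures reproduce.

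**2. The two windows for a completer.**

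| | Starts | Ends |
|---|---|---|
| Protocol 9.4.1, primary safety analysis | first dose | end of taper, about Day 400 |
| SAP 3.2.1.3 and 5.12.1, TEAE summaries | first dose | last follow-up contact, about Day 428 |

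The difference is 28 days. As a share of the SAP window, 28/428 = 6.5% (28/427 = 6.6% on elapsed days). Taper plus follow-up is 428 − 379 = 49 days, and 49/427 = 11.5%. The taper alone is 21/399 = 5.3% of the Treatment Period.

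**3. Early stoppers.** The documents give no dropout rate, so the stopping times are assumed. With d days before the decision to stop, 21 days of taper and 28 days of follow-up, the off-drug share is 28/(d + 49):

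| d (assumed) | Off-drug share |
|---|---|
| 14 | 28/63 = 44% |
| 30 | 28/79 = 35% |
| 91 | 28/140 = 20% |
| 182 | 28/231 = 12% |

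Without taper, Protocol Section 7.3 places the Visit 17 assessments about 30 days after the last dose. For an assumed stop at Day 30, the share is about 30/60 = 50%.

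**4. From time to incidence (illustration only).** Assume that all 120 expected subjects complete, that the event rate is constant on treatment, and that 10% have the event within 57 weeks. The weekly rate is h = −ln(0.90)/57. If the off-drug rate is m times h, incidence over 61 weeks is 1 − exp(−57h − 4mh):

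| m (assumed) | Incidence, 61 weeks | Subjects of 120 (12.0 at 57 weeks) |
|---|---|---|
| 1 | 10.7% | 12.8 |
| 3 | 12.0% | 14.4 |
| 5 | 13.3% | 15.9 |

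**5. Can dose at onset stand in for phase?** From Protocol Table 4 and SAP Table 1:

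- 17.5 mg BID is the second titration week for subjects from the 7.5 mg arm, the reduced maintenance dose, and the first taper week from 25 mg.
- 5 mg BID is the first titration week for former placebo subjects and also a taper dose.
- No category or rule is given for an event after the last dose.

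The presentation therefore cannot reconstruct the Treatment Period or isolate taper and off-drug events.

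**The case against.** The best defence is that the tension starts inside the protocol. Its TEAE definition is open-ended, AEs are collected to Day 428, and the summaries listed in Section 9.4.1 are all TEAE summaries. Section 9.4 also calls itself a summary of the planned analyses. This stands in part: the SAP window is compatible with the protocol's TEAE definition. It does not answer the sentence that names the primary analysis and its period.

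A reader might infer several stronger points that the documents do not support:

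- *That the SAP offers no breakdown at all.* It plans one by dose at onset and lists every AE by subject. The breakdown is incomplete, not absent.
- *That withdrawal effects would be hidden.* The mCIWA-B is scheduled from Day 379 to Day 428 and summarised by visit with change from Day 379 (SAP Section 5.12.8). It is a symptom score and does not classify reported AEs by period, but withdrawal is not left unexamined.
- *That off-drug means withdrawal.* The taper lies inside the Treatment Period, so the protocol's own window also mixes dose-reduction events with full-dose events.
- *That SAP Section 6 conceals a change.* It concerns departures from the SAP itself and does not claim to list differences from the protocol. Its silence shows little.

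The trial is also single-arm with no test, so no between-arm comparison is biased.

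**Conclusion.** The point holds as an omission: following the SAP as written does not yield the protocol's named primary safety summary. The mismatch is 28 days for a completer, about 6.5% of the TEAE window, and a larger share for anyone who stops early.

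The 35% and 50% figures should not be read as bias in the AE percentages. They are shares of follow-up time for one assumed stopping day. The effect on incidence depends on how many subjects stop early and on the off-drug event rate, and the documents give neither. For completers it is modest unless events cluster after the last dose. In the 10% illustration it ranges from 0.7 to 3.3 percentage points, on assumed rate ratios of 1 to 5.

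The change is worth making before database lock, because it concerns the primary objective and the remedy is simple.

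**What to change.** In SAP Section 5.12.1:

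1. Make the primary TEAE tables (all, by severity, related, serious) cover onset in the Treatment Period, from first through last dose of IMP. SAP Section 4.1.12 already defines the last dose, and Section 3.2.7.1 already uses it to mark medications as post-treatment.
2. Add separate columns for onset during taper and for onset after the last dose through Visit 17. The taper column is needed because a first-to-last-dose column alone would still mix taper with full-dose events.
3. Keep the all-period total, which preserves the current TEAE definition.
4. In the dose-at-onset presentation, define explicit taper and off-drug categories.

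The cost is a paragraph of SAP text and a few more columns in tables already planned, with no new data. The primary percentages may be slightly lower than the all-period ones, so both should be labelled with their windows. If the sponsor prefers the longer window as primary, the SAP should say so, give the reason, and note the difference from Protocol Section 9.4.1.
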